6.4 Exploratory Analyses

Analyses for exploratory endpoints will be performed using the mITT or safety populations.

Exploratory dichotomous response variables will be summarized in a manner similar to that used for the secondary efficacy analyses. In addition, summaries of ≥ 1 stage improvement, no change, and worsening will be tabulated and graphically presented for NASH CRN Fibrosis Score, Ishak Fibrosis Score, and NAS Total at Week 24. For these analyses, participants without a Week 24 or ET result will be classified into the "Worse" category for these exploratory summaries.

Early termination visits for non-biopsy endpoints such as imaging and biomarkers may occur at other time points and will not be summarized together with Week 24. For non-biopsy endpoints, ET will be summarized separately in the summary tables. Imputation on missing data will not be performed for non-biopsy endpoints.

Summary statistics will be tabulated for all treated subjects by treatment and by Visit. Continuous data will be summarized using n, mean, standard deviation, median, minimum, and maximum.

Analysis of covariance (ANCOVA) model will be used to explore change from baseline for endpoints having a baseline and a post-baseline values.

Repeated measures analysis will model the change from baseline for the endpoint in presence of repeated measurements taken at various timepoints on/before the analysis visit.

Sponsor: Bristol-Myers Squibb

Protocol no: MB130-068

The model will include treatment group, visit, baseline value, treatment * visit and baseline stratification factors as main effects. An unstructured covariance matrix will be used to represent the correlation of the repeated measures within each subject. The model will provide point estimates, standard errors and 2-sided 95% confidence intervals for mean change from baseline at by time points.

Other biomarkers will be descriptively summarized by time point and will include percent change from baseline in addition to change from baseline. Exploratory endpoints assessing relationships will be graphically presented.

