8.3.1 Inclusion Criteria

1. Signed written informed consent
 - a) Participants must be willing to participate in the study and sign the informed consent form(s) (ICF[s])
 - b) Participants (and caregivers as applicable) must be willing and able to complete all study-specific procedures and visits
2. Liver biopsy performed within 6 months (26 weeks) prior to the Screening Period. Biopsy performed prior to ICF must be available to the central reader prior to randomization. If historical biopsy is not available, a liver biopsy will be performed during the Screening Period (see [Section 8.5.1.1](#)). Biopsy must be consistent with NASH, with:
 - a) A score of at least 1 for each NAS component (steatosis, lobular inflammation, and ballooning), as assessed by the central reader
AND
 - b) Stage 3 liver fibrosis according to the NASH CRN classification, as assessed by the central reader
3. Participants taking anti-diabetic, anti-obesity, or anti-dyslipidemic medications must have been on stable regimens for at least 3 months (12 weeks) (6 weeks for statins) prior to and during the Screening Period. The investigator may contact the medical monitor regarding the stability of a participant's regimen when determining eligibility for study participation. Participants taking vitamin E at doses ≥ 800 IU/day must have been on stable doses for at least 6 months (26 weeks) prior to and during the Screening Period. Vitamin E treatment (≥ 800 IU/day) must not have been initiated after the qualifying liver biopsy was performed.

4. Age and reproductive status
 - a) Men or women 18 to 75 (inclusive) years of age
 - b) Women of childbearing potential (WOCBP) must have a negative pregnancy test (minimum sensitivity 25 IU/L or equivalent units of human chorionic gonadotropin) within 24 hours prior to the start of study medication
 - c) Women must not be breastfeeding at any time during the study
 - d) WOCBPs must agree to follow instructions for method(s) of contraception for the duration of treatment (BMS-986036 or placebo) plus 5 half-lives of study medication (5 days) plus 30 days (duration of ovulatory cycle) for a total of 35 days after the end of the Double-Blind Treatment Period
 - e) WOCBPs who are continuously not heterosexually active are exempt from contraceptive requirements but must undergo pregnancy testing as described in the Schedule of Activities in [Section 1](#)

[figure not shown]

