4.0 Endpoints

4.1 Primary Efficacy Endpoint

The primary efficacy endpoint of this study is the proportion of participants who achieve a ≥ 1 -stage improvement (as defined by NASH CRN Fibrosis Score) in fibrosis without worsening of NASH or NASH improvement (as defined by NAS) with no worsening of fibrosis (as defined by NASH CRN Fibrosis Score) at Week 24 as determined by liver biopsy.

For this protocol, improvement in fibrosis is defined as a decrease of fibrosis by ≥ 1 point, as determined by the NASH CRN Fibrosis Score. Worsening of fibrosis is defined as an increase of fibrosis by ≥ 1 point, as determined by the NASH CRN Fibrosis Score. Worsening of NASH is defined as an increase of the NAFLD Activity Score (NAS) by ≥ 1 point. NASH improvement is defined as a decrease of NAS by ≥ 2 points (with contribution from > 1 NAS component).

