4.2 Secondary Efficacy Endpoints

The secondary efficacy endpoints are the proportion of participants with the following:

- NASH CRN Fibrosis Score $>=1$ stage improvement at Week 24
- Ishak Score $>=1$ stage improvement at Week 24
- Any CPA decrease at Week 24
- NASH resolution (NAS component of ballooning = 0 and inflammation = 0-1) without worsening of fibrosis (as defined by NASH CRN Fibrosis Score) at Week 24
- NASH resolution (NAS component of ballooning = 0 and inflammation = 0-1) at Week 24
- NASH improvement (reduction of NAS by ≥ 2 points with contribution from > 1 NAS component) without worsening of fibrosis at Week 24
- Achieve a ≥ 1 -stage improvement (as defined by NASH CRN Fibrosis Score) in fibrosis without worsening of NASH
- NASH improvement (reduction of NAS by ≥ 2 points with contribution from > 1 NAS component) at Week 24
- Progression to cirrhosis (as defined by NASH CRN Fibrosis Score) at Week 24

Sponsor: Bristol-Myers Squibb

Protocol no: MB130-068

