4.5 Exploratory Endpoints

Exploratory endpoints include the following:

- Quantitative measurements of fibrosis and fat on biopsy
 - Assessment of NASH CRN Fibrosis Score at Week 24
 - Proportion of participants with >=2 stage improvement
 - Changes in Fibrosis (as expressed by Shift from baseline)
 - Proportion of participants with >=1 stage improvement, no change, or worsening
 - Assessment of Ishak Fibrosis Score at Week 24
 - Proportion of participants with >=2 stage improvement
 - Changes in Fibrosis (as expressed by Shift from baseline)
 - Proportion of participants with >=1 stage improvement, no change, or worsening
 - Assessment of Fibrosis and NASH using digital pathology at Week 24
 - Absolute, percent change, and change from baseline
 - Assessment of CPA at Week 24
 - Proportion of participants with any improvement
 - Absolute, percent change, and change from baseline
 - Assessment of fat in stained tissue by morphometry and alpha smooth muscle actin (SMA) at Week 24
 - Absolute, percent change, and change from baseline
- Assessment of NAS score at Week 24
 - Changes in NAS (as expressed by shift from baseline, for each individual NAS components (Steatosis, inflammation, Ballooning) as well as Total score)

Sponsor: Bristol-Myers Squibb

[figure not shown]
Protocol no: MB130-068

- Proportion of participants with improvement, no change, or worsening in NAS Total
- Assessment of NASH using digital pathology
 - Absolute, percent change, and change from baseline
- Hepatic fat fraction as measured using MRI-PDFF at Week 24 and Week 48
 - Absolute, percent change, and change from baseline
 - Proportion of subjects in each treatment group with $\geq 30\%$ relative reduction, $\geq 20\%$ relative reduction, $\geq 10\%$ relative reduction, and $\geq 5\%$ absolute reduction
- Noninvasive measures of fibrosis and/or cirrhosis
 - Liver stiffness as determined by Magnetic Resonance Elastography (MRE) at Week 24 and Week 48
 - Absolute, percent change, and change from baseline
 - Proportion of subjects in each treatment group with $\geq 19\%$ or $\geq 15\%$ reduction
- Noninvasive scores of hepatic fibrosis (AST-Platelet Ratio Index (APRI), Fibrosis 4 (FIB-4), Enhanced Liver Fibrosis (ELF), and NAFLD Fibrosis Score) from Day 1 to Week 24 and Week 48
 - Absolute, percent change, and change from baseline
 - Proportion of participants in each ELF category by time point
- Metabolic assessments at Week 24 and Week 48

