8.6 Liver Biopsy Scoring

Histological assessment of the liver tissue sample will be conducted by a blinded Central Pathologist. The central reader will be a medical doctor, board certified in pathology, with experience in liver pathology in a clinical study setting. Additional details on the acquisition, quality requirements, histological preparation, and shipping of histological samples are in the Central Laboratory Manual and the Central Pathology Manual or Charter.

Histological Scoring

NASH CRN

For associated primary and secondary endpoints, the NASH CRN system will be used to score the histologic samples and results are reported as the NAFLD Activity Score (NAS) and the NASH CRN Fibrosis Score. The NASH CRN system is based on the concept that necroinflammatory lesions and stage of fibrosis should be evaluated separately; it assesses liver biopsies for degree of steatosis (0-3), lobular inflammation (0-3), hepatocellular ballooning (0-2), and fibrosis (0-4).

Sponsor: Bristol-Myers Squibb

Protocol no: MB130-068

NAS

The 3 categories of steatosis, lobular inflammation, and ballooning scores are added together in an unweighted fashion to determine the NAS, which ranges from 0 to 8 (see table below).

Histology Variable	Grade	Score
Steatosis	< 5%	0
	5%-33%	1
	> 33% - 66%	2
	> 66%	3
Lobular Inflammation ^a	none	0
	< 2	1
	2 - 4	2
	> 4	3
Ballooning	none	0
	few	1
	many	2

NAS = NAFLD Activity Score

^a Foci per x200 field

Fibrosis

NASH CRN Fibrosis

Fibrosis is staged separately from NAS on a 0-4 scale: 0 (none); 1 (perisinusoidal or periportal fibrosis); 2 (perisinusoidal and portal/periportal fibrosis); 3 (bridging fibrosis); 4 (cirrhosis).

Participants will be evaluated for progression to cirrhosis (NASH CRN Fibrosis stage 3 to stage 4) at Week 24.

Ishak

A modified Ishak scoring system will also be used to stage fibrosis in the histologic samples. The Ishak system (0-6 scale) was originally developed to grade portal-based liver fibrosis associated with viral hepatitis. The modified Ishak system has been adapted to stage central-based liver fibrosis associated with NASH, and it also uses a 0-6 scale:

- 0: No fibrosis
- 1: centrilobular pericellular fibrosis
- 2: centrilobular and periportal fibrosis
- 3: bridging fibrosis (few bridges)
- 4: bridging fibrosis (many bridges)
- 5: early or incomplete cirrhosis
- 6: established or advanced cirrhosis

Sponsor: Bristol-Myers Squibb

Protocol no: MB130-068

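### SAP 6.4 counts missing Week 24/ET biopsies as *Worse*, so the exploratory worsening rows mix absent data with observed deterioration and, for NASH CRN, can disagree with progression to cirrhosis

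*SAP*

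**What the plan says.** SAP 4.5 lists, for each fibrosis scale, the endpoint "Proportion of participants with >=1 stage improvement, no change, or worsening", with a similar item for total NAS. SAP 6.4 says that summaries of improvement, "no change, and worsening will be tabulated and graphically presented for NASH CRN Fibrosis Score, Ishak Fibrosis Score, and NAS Total at Week 24". It then adds, for these exploratory summaries, that "participants without a Week 24 or ET result will be classified into the 'Worse' category". No category for missing results is named.

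Elsewhere worsening is a measured change. SAP 4.1 has "Worsening of fibrosis is defined as an increase of fibrosis by ≥ 1 point, as determined by the NASH CRN Fibrosis Score" and "Worsening of NASH is defined as an increase of the NAFLD Activity Score (NAS) by ≥ 1 point".

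Four other places bear on the NASH CRN table:

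- Protocol 8.3.1 requires "Stage 3 liver fibrosis according to the NASH CRN classification, as assessed by the central reader" at entry.
- SAP 4.2 lists as a secondary endpoint "Progression to cirrhosis (as defined by NASH CRN Fibrosis Score) at Week 24", and SAP 8.6 explains it: "Participants will be evaluated for progression to cirrhosis (NASH CRN Fibrosis stage 3 to stage 4) at Week 24".
- SAP 6.1.2 analyses secondary endpoints by the primary method, and SAP 6.1.1 treats a missing biopsy as non-response for the primary endpoint. No rule is stated specifically for progression.
- SAP 7.2 bases the Week 24 efficacy summaries on participants who have completed liver biopsy.

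**The concern.** Counting a missing biopsy as non-response withholds a benefit that was not shown. Counting it as *Worse* asserts a harm that was not seen, and puts participants under a definition against which they were never assessed.

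Two things follow. First, the *Worse* percentage rises with the missing-biopsy rate, and a difference between arms in that rate reads as a difference in histological deterioration. Missing biopsies are foreseeable: under Protocol 8.5.1.1, a participant who leaves the study before Week 20 is only asked to consider a biopsy at ET. Second, the only possible worsening from NASH CRN stage 3 is stage 4, which is progression to cirrhosis. The same unbiopsied participant could be *Worse* in one table and not progressed in another, so the report would carry two different figures for one event.

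**Working it through.** **The plan's own figure.** The only design figure stated is at least 80% power for the primary trend test (SAP 2.2: 15/20/30/40%, 40 per arm, one-sided 0.05). A normal approximation gives 86.8% with equally spaced scores and 86.1% with dose scores, so the statement holds. The rule in SAP 6.4 does not enter that calculation. The documents give no missing-biopsy rate and no expected worsening rate, so the values below are assumptions: m from 5% to 25%, w from 5% to 20%.

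**Formulae**, as fractions of the mITT arm:

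- *Worse* under SAP 6.4 = m + (1 − m)w.
- Progression to cirrhosis with missing = not met (SAP 6.1.1 carried over by 6.1.2) = (1 − m)w.
- The gap between them is exactly m, whatever w is.
- If progression were instead reported among biopsied participants only, it would equal w and the gap would be m(1 − w).

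**NASH CRN, w = 10%:**

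| m | *Worse* | Progression (missing = not met) | Gap, points |
|---|---|---|---|
| 5% | 14.5% | 9.5% | 5 |
| 10% | 19.0% | 9.0% | 10 |
| 15% | 23.5% | 8.5% | 15 |
| 20% | 28.0% | 8.0% | 20 |
| 25% | 32.5% | 7.5% | 25 |

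At the ends of the assumed ranges, *Worse* is 0.05 + 0.95 × 0.05 = 9.75% and 0.25 + 0.75 × 0.20 = 40.0%.

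**Unequal missingness, w = 10% in every arm.** With 8% missing in one arm and 20% in another, *Worse* is 0.08 + 0.92 × 0.10 = 17.2% against 0.20 + 0.80 × 0.10 = 28.0%, a 10.8-point difference with no true difference in worsening. If missingness ran 5/8/12/20% from placebo to 40 mg, *Worse* would run 14.5/17.2/20.8/28.0% (+13.5 points, 40 mg against placebo). Progression with missing = not met would run 9.5/9.2/8.8/8.0% (−1.5 points). The two displays would point in opposite directions.

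**Counts in one arm of 49.** Assume 10 improved, 28 unchanged, 4 at stage 4 and 7 without a biopsy.

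| Row | SAP 6.4 | Separate missing row | Among 42 biopsied |
|---|---|---|---|
| Improved | 10/49 = 20.4% | 10/49 = 20.4% | 10/42 = 23.8% |
| No change | 28/49 = 57.1% | 28/49 = 57.1% | 28/42 = 66.7% |
| Worse | 11/49 = 22.4% | 4/49 = 8.2% | 4/42 = 9.5% |
| No biopsy | – | 7/49 = 14.3% | – |

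On the mITT denominator only the *Worse* row moves. With the separate row, its count of 4 matches the observed stage 3-to-4 count.

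**Interaction with SAP 7.2.** If the Week 24 summaries contain only participants with a completed biopsy, the rule has little to act on at that lock. If instead all 197 were kept in the denominator when about 160 had been reached, up to 37/197 = 18.8% could be labelled *Worse*. The two sections do not say which applies.

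**The case against.** The strongest defence is that the rule is pre-specified, is confined to exploratory summaries for which no test is planned, and is a recognisable worst-case convention. If missingness were higher on active drug, it would count against the sponsor's product. Other outputs limit the damage. SAP 4.5 plans shift tables on the same scales, SAP 6.1.1 lists all biopsy results, ET biopsies count, and SAP 7.2 accepts biopsies delayed to between Week 24 and Week 48. Table labels sit in shells that are not part of these documents.

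This fairly limits the consequence, but it does not rescue the label. A worst-case convention belongs in a marked sensitivity summary, not in the only stated version of the three-category display. The shift tables carry no stated rule for missing results, and the completer analysis is planned for the primary variable only.

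A reader might also infer more than the documents support:

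- **That the no-change row is wrong too.** It is not: the rule moves nobody into or out of it on the mITT denominator.
- **That drug-related dropout will make missingness differ by arm**, given gastrointestinal AEs of 72% on drug and 28% on placebo in Phase 2a. The same section (Protocol 6.3.2.1) reports no discontinuations for such events and none of severe intensity.
- **That the *Worse* row would consist mostly of missing biopsies.** That depends on assumed inputs. At w = 10% and m = 8%, 9.2 of the 17.2 points are observed worsening.
- **That all three tables conflict with progression to cirrhosis.** Only NASH CRN can; a move from Ishak 3 to 4 or a rise in NAS is not cirrhosis.

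**Conclusion.** The concern stands as a reporting fault in exploratory displays. In all three tables the *Worse* row is inflated above the worsening rate among biopsied participants, by m(1 − w): for example from 10% to 19–28% at m = 10–20%. It also turns any imbalance in missing biopsies into an apparent imbalance in deterioration. Neither m nor w is in the documents, so the size is illustrative; the direction is not, whenever m is above zero.

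The disagreement with progression to cirrhosis is confined to NASH CRN and rests on inference. It equals m if SAP 6.1.2 carries the missing = not met rule over to that endpoint. It disappears only if non-response is read as having progressed, and then unobserved cirrhosis would enter a secondary endpoint. The SAP should say which reading holds.

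The primary and secondary tests and the improvement row are untouched. At the Week 24 lock the effect may be small, depending on how SAP 7.2 is read. The rule should be changed, but it does not threaten the trial's main conclusion.

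**What to change.** In SAP 6.4, replace the imputation sentence with a fourth category, no Week 24/ET biopsy, on the mITT denominator. Alongside it:

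1. Show the three observed categories also as percentages of biopsied participants.
2. State in SAP 6.1.2 how a missing biopsy is handled for progression to cirrhosis, so that the NASH CRN worsening count matches that endpoint's event count.
3. Reconcile SAP 6.4 with SAP 7.2 on who is in the denominator of the Week 24 summaries.
4. If a missing = worse version is still wanted, keep it only as a labelled worst-case sensitivity summary.

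The cost is a few sentences in the SAP and one extra row per table and graph. No new data are needed, and neither the improvement row nor any planned test of the primary endpoint changes.

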 - Fasting plasma glucose
 - Fasting plasma insulin
 - Hemoglobin A1c
- Exploratory Biomarkers (see [Section 8.5.4](#))
 - Transaminases at each visit through Week 52/PTFU
 - Adiponectin at Day 1, Week 4, Week 8, Week 12, Week 24, Week 48 (or the ET Visit, if applicable) and Week 52/PTFU
 - PRO-C3 at Day 1, Week 4, Week 8, Week 12, Week 24, and Week 48 (or the ET Visit, if applicable) and Week 52/PTFU
- Health-related quality-of-life (HRQoL) questionnaires (see [Section 8.5.1.6](#)) at Day 1, Week 24, and Week 48 (or the ET Visit, if applicable)
 - 3-Level EuroQol 5 Dimension (EQ-5D-3L) questionnaire
 - 36-question Short Form (SF-36) quality-of-life questionnaire

- Chronic Liver Disease Questionnaire-Nonalcoholic Fatty Liver Disease (CLDQ-NAFLD) questionnaire

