Any pregnancy that occurs in a female partner of a male study participant should be reported to sponsor or designee during at least 5 half-lives after product administration (5 days) plus 30 days (duration of ovulatory cycle) for a total of 35 days after the end of the Double-Blind Treatment Period. In order for the sponsor or designee to collect any pregnancy surveillance information from the female partner, the female partner must sign an ICF for disclosure of this information. Information on this pregnancy will be collected on the Pregnancy Surveillance Form.

Laboratory Test Result Abnormalities

The following laboratory test result abnormalities should be captured on the nonserious AE eCRF page or SAE eCRF page, as appropriate. Paper forms are to be used only in the event that the electronic system is not functioning.

- Any laboratory test result that is clinically significant or meets the definition of an SAE
- Any laboratory test result abnormality that required the participant to have study medication discontinued or interrupted
- Any laboratory test result abnormality that required the participant to receive specific corrective therapy

It is expected that wherever possible, the clinical rather than laboratory term would be used by the reporting investigator (e.g., anemia versus low hemoglobin value).

Potential Drug-Induced Liver Injury

Wherever possible, timely confirmation of initial liver-related laboratory abnormalities should occur prior to the reporting of a potential DILI event. All occurrences of potential DILIs, meeting the defined criteria, must be reported as SAEs (see Appendix 8 for reporting details). **Repeat laboratory testing may be performed locally**, and the results should be promptly communicated to the investigator site.

For the purpose of evaluating a potential DILI, the Baseline value is defined as the mean of the test results from analysis of samples collected during Screening and on Day 1.

Note that the evaluation processes below do not replace SAE reporting per defined criteria in [Appendix 8](#).

Evaluation of Participants with New Elevations of Aminotransferases and/or Total Bilirubin

Repeat laboratory testing (including ALT, AST, fractionated bilirubin and alkaline phosphatase) and physical examination should be performed within 48-72 hours when:

- Participants with normal Baseline aminotransferase (ALT and/or AST) values develop elevations greater than $3\times$ the ULN based upon the central lab, or

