
ELF Assay (to be collected at Day 1, Week 24, Week 48, and ET [if applicable]). Participants will fast for 8 hours prior to collection of blood samples for these assessments:
 
• Hyaluronic acid• Procollagen 3 amino terminal peptide• Tissue inhibitor of metalloproteinases 1 (TIMP-1)

Laboratory Metabolic Markers (to be collected at Screening, Day 1, Week 24, Week 48, and ET [if applicable]). Participants will fast for 8 hours prior to collection of blood samples for these assessments:
 
• Low-density lipoprotein cholesterol• High-density lipoprotein cholesterol• Triglycerides• Plasma glucose – Also used for NAFLD Fibrosis Score.• Plasma insulin• Hemoglobin A1c – also to be collected at Long Term Immunogenicity Follow Up Visits as applicable (see Section 8.5.3.6)

Hepatitis Assessments (to be collected at Screening only- see Appendix 3 for diagnosis and exclusion criteria):
 
• Hepatitis B core antigen antibody• Hepatitis B surface antigen antibody• Hepatitis B surface antigen• Hepatitis B virus DNA• Hepatitis C virus antibody• Hepatitis C virus RNA

Pregnancy Testing (to be collected at each visit through the Week 52/PTFU Visit):
 
• Serum or urine β-HCG. Women of childbearing potential only. Serum β-HCG to be collected at Screening and serum or urine β-HCG to be collected thereafter according to local laws and regulations and Institutional Review Board/Ethics Committee requirements)• Follicle-stimulating hormone (Screening only for postmenopausal women)

Hematology (to be collected at each visit through the Week 52/PTFU Visit):
 
• Complete Blood Count
◦ White blood cells, including differential◦ Red blood cells

- Hemoglobin
- Hematocrit
- Platelet count – *Also used for FIB4, APRI, and NAFLD Fibrosis Score.*
- Mean corpuscular hemoglobin (MCH)
- Mean corpuscular hemoglobin concentration (MCHC)
- Red cell distribution width (RDW)
- Prothrombin time
- Partial thromboplastin time
- International normalized ratio

Blood Chemistry (to be collected at each visit through Week 52/PTFU and at Long-Term Immunogenicity Follow-Up Visits as applicable [see Section 8.5.3.6]):

- AST – *Used as both safety and efficacy endpoints. Also used for FIB4, APRI, and NAFLD Fibrosis Score*

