- ALT – *Used as both safety, efficacy endpoints, and for FIB4, APRI, and NAFLD Fibrosis Score*
- Serum glucose
- Total bilirubin
- Indirect bilirubin
- Alkaline phosphatase
- Lactate dehydrogenase
- Creatinine
- Blood Urea Nitrogen
- Uric acid
- Total Protein
- Albumin – *Also used for NAFLD Fibrosis Score.*
- Sodium
- Potassium
- Chloride
- Carbon dioxide
- Calcium
- Phosphorus
- Glomerular filtration rate

Urinalysis (to be collected at each visit through the Week 52/PTFU Visit):

- pH
- Specific gravity
- Protein [REDACTED]
- Glucose
- Ketones
- Blood
- Leukocyte esterase
- Nitrite
- Creatinine [REDACTED]
- Albumin [REDACTED]
- Microscopic examination (only to follow-up abnormal findings)
- Drug Screen (Screening only)

Immunogenicity (to be collected at Day 1 and each subsequent visit through the Week 52/PTFU Visit and at Long-Term Immunogenicity Follow-Up Visits as applicable [see Section 8.5.3.6]):

- Serum anti-BMS-986036 antibody
- Serum anti-FGF21 antibody

PRO-C3 (to be collected at Screening, Day 1, Week 4, Week 8, Week 12, Week 24, Week 48, ET [if applicable], and Week 52/PTFU). Participants will fast for 8 hours prior to collection of blood samples for these assessments:

- N-terminal type 3 collagen propeptide (PRO-C3) – Will include blood collection for additional serum for new or improved assays

Adiponectin (to be collected at Screening, Day 1, Week 4, Week 8, Week 12, Week 24, Week 48, ET [if applicable], and Week 52/PTFU). Participants will fast for 8 hours prior to collection of blood samples for these assessments

Plasma and Serum for disease, target and drug effect biomarkers (to be collected at Day 1, Week 4, Week 8, Week 12, Week 24, Week 48, ET [if applicable], Week 52/PTFU, and 6 months after Week 52/PTFU). Participants will fast for 8 hours prior to collection of these samples

Gene Expression (to be collected at Screening, Day 1, Week 4, Week 8, Week 12, Week 24, Week 48, ET [if applicable], and Week 52/PTFU):

- Whole blood for RNA analysis (broad and/or directed gene expression profiling)

Micro RNA (miRNA) (to be collected at Screening, Day 1, Week 4, Week 8, Week 12, Week 24, Week 48, ET [if applicable], and Week 52/PTFU)

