8.0 Conventions and General Definitions

8.1 General Definitions

Term	Definition
Study Day	Study day is calculated as: assessment date – date of first dose + 1
Baseline	Unless otherwise stated, Baseline is defined as the last measurement prior to dosing on Day 1 (Week 0). If the measurement on Day 1 is missing or not available, then a prior measurement during the screening period may be used as baseline.
Change from Baseline	Change = Value at post-baseline visit – value at baseline
Change in the maximum post-baseline value	Change = Highest observed value post-baseline – value at baseline
Percent Change from Baseline	Percent change from baseline is defined as ([value at post-baseline visit – value at baseline]/value at baseline) x 100. If the baseline value is 0 and the post-baseline value is also 0, then the percent change from baseline is set to 0.
Study Treatment	For the purposes of the calculations included in this SAP, study treatment will include only doses of BMS-986036 (dose levels of 10 mg QW, 20 mg QW or 40 mg QW) or placebo QW.
Duration of Study Treatment	Duration of study treatment in weeks will be defined as: (date of last dose of study treatment – date of first dose of study treatment+7)/7.
Treatment Completion (%)	Treatment completion (%) will be calculated as the total number of treatment doses received divided by the total number of expected doses (48), multiplied by 100.
End of Study (EOS) Date	The EOS date is the date recorded on the eCRF that a participant either discontinued or completed the study. If the participant is lost to follow-up, the EOS date will be the date of the last visit assessment obtained.
First Dose Date – Study	The date a participant received their first dose as recorded in the eCRF as date study treatment was administered.
Last Dose Date – Study	The date of last recorded dose on the eCRF for a subject.
Unscheduled assessments	Unscheduled measurements will be included in the listings. With the exception of unscheduled measurements used for baseline and unscheduled measurements will be excluded from the descriptive statistics and statistical analysis.

Sponsor: Bristol-Myers Squibb

Protocol no: MB130-068

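### For markers measured at both Screening and Day 1, the exploratory models adjust for one pre-dose value only; adding the second could cut residual variance by anything from 0 to about 20%

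*SAP*

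**What the plan says.** SAP 6.4 plans an ANCOVA and a repeated-measures model for change from baseline in exploratory endpoints. The covariate list follows the repeated-measures description: "The model will include treatment group, visit, baseline value, treatment * visit and baseline stratification factors as main effects". The ANCOVA has no list of its own. No baseline-by-visit term appears, so the baseline slope is the same at every visit.

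SAP 8.1 fixes what baseline means: "Baseline is defined as the last measurement prior to dosing on Day 1 (Week 0"). The Screening value is a fallback only: "If the measurement on Day 1 is missing or not available, then a prior measurement during the screening period may be used as baseline".

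The Protocol collects two pre-dose values for many of these markers. Table 8 in section 8.5.4 has "PRO-C3 (to be collected at Screening, Day 1, Week 4, Week 8, Week 12, Week 24, Week 48" and "Adiponectin (to be collected at Screening, Day 1, Week 4, Week 8, Week 12", and lists the laboratory metabolic panel (LDL, HDL, triglycerides, glucose, insulin, HbA1c) at both visits. Tables 1 and 2 mark blood chemistry (hence ALT and AST), weight and waist at both. The list in Protocol 8.5.1 disagrees on two markers: it has "PRO-C3 at Day 1, Week 4, Week 8, Week 12, Week 24, and Week 48", and adiponectin likewise, with no Screening sample.

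For potential drug-induced liver injury only, Protocol 8.5.3.1 uses both samples: "the Baseline value is defined as the mean of the test results from analysis of samples collected during Screening and on Day 1".

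**The concern.** A single pre-dose value carries within-person noise. A second pre-dose value, if it says anything about follow-up beyond what Day 1 says, removes residual variance at no further cost to participants. Both values precede dosing, so adjusting for both introduces no bias.

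Precision is worth having here. There are 197/4 ≈ 49 participants per arm in total, and about 160/4 = 40 per arm in the Week 24 analysis described in SAP 7.2. Protocol 6.2.1 says PRO-C3 is measured to learn about its potential as a pharmacodynamic marker of fibrosis, and that Phase 3 design and dose selection will rest on the totality of the efficacy, safety and PK analyses from this study and MB130-069.

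**Working it through.** **The plan's own figure.** There is none to reproduce. Neither document gives a variance, a within-person correlation or a power figure for the exploratory models. The only power statement (SAP 2.2, at least 80%) concerns the trend test on the primary biopsy endpoint, which this point does not affect. All correlations below are therefore assumptions.

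**Notation.** r1 = correlation of Day 1 with follow-up; r2 = Screening with follow-up; r12 = Screening with Day 1. Variances are set to 1.

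**General formula.** The proportional fall in residual variance from adding Screening to a model that already holds Day 1 is the squared partial correlation:

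(r2 − r1·r12)² / [(1 − r1²)(1 − r12²)].

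It cannot be negative. The only loss is degrees of freedom.

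**Case A: all three correlations equal r.** One baseline leaves 1 − r²; two leave 1 − 2r²/(1 + r); the fall is r²/(1 + r)².

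| r | one baseline | two baselines | fall | smaller SE | equivalent extra participants |
|---|---|---|---|---|---|
| 0.5 | 0.750 | 0.667 | 11.1% | 5.7% | 12.5% |
| 0.6 | 0.640 | 0.550 | 14.1% | 7.3% | 16.4% |
| 0.7 | 0.510 | 0.424 | 17.0% | 8.9% | 20.4% |
| 0.8 | 0.360 | 0.289 | 19.8% | 10.4% | 24.6% |

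At r = 0.3 the fall is 5.3%; at r = 0.9 it is 22.4%. In 3,000 simulated four-arm ANCOVAs with N = 197, the variance of a treatment difference fell 10.6% (r = 0.5) and 19.3% (r = 0.8), so the extra covariate costs about half a percentage point.

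**Case B: the two pre-dose values resemble each other more than either resembles follow-up.** With r1 = r2 = r the formula becomes r²(1 − r12)/[(1 − r²)(1 + r12)].

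- r = 0.5, r12 = 0.8: 0.25 × 0.2/(0.75 × 1.8) = 3.7%
- r = 0.6, r12 = 0.8: 0.36 × 0.2/(0.64 × 1.8) = 6.3%
- r = 0.7, r12 = 0.8: 0.49 × 0.2/(0.51 × 1.8) = 10.7%
- r = 0.5, r12 = 0.9: 0.25 × 0.1/(0.75 × 1.9) = 1.8%
- r = 0.6, r12 = 0.9: 0.36 × 0.1/(0.64 × 1.9) = 3.0%
- r = 0.7, r12 = 0.9: 0.49 × 0.1/(0.51 × 1.9) = 5.1%

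**Case C: Screening also predicts follow-up less well than Day 1.** Take r1 = 0.7 and r12 = 0.8, so the denominator is 0.51 × 0.36 = 0.1836.

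- r2 = 0.65: (0.65 − 0.56)²/0.1836 = 4.4%
- r2 = 0.60: (0.60 − 0.56)²/0.1836 = 0.9%
- r2 = 0.56 = r1·r12 (pure serial decay): 0%

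**The form of adjustment matters.** Suppose the response stays change from Day 1 and the Day 1 covariate is replaced by the mean of the two samples. With equal correlations the residual variance is 2(1 − r) − (1 − r)²/[2(1 + r)].

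- r = 0.5: 1 − 0.25/3 = 0.917, against 0.750 now, a rise of 22%
- r = 0.8: 0.4 − 0.04/3.6 = 0.389, against 0.360 now, a rise of 8%

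Simulation gave the same 22% and 8%. Screening should therefore enter alongside Day 1 as its own covariate.

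**The case against.** The strongest reply is that this is a preference. Adjusting for the last pre-dose value is unbiased and conventional, and it matches the Day 1 predose reference that SAP 4.5 uses for change in ALT, AST and PRO-C3. The analyses are exploratory. All of that stands, and it is why the point is minor.

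The second reply is that Screening may add little, and the Protocol gives reasons. Screening can run 8 weeks, or 12 by agreement (8.1). Diet, exercise and weight counselling is given at Screening (8.3.6). Eligibility limits act on Screening values of ALT, AST, glucose, HbA1c and triglycerides (8.3.2). T2DM status is already in the model through the strata and may absorb part of the gain for glucose and HbA1c. This also stands, and it puts the lower end of the range at zero.

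Third, the Screening value is not unique. Tests may be repeated (8.3.8.1) and results may be carried over from MB130-069 (8.3.8.2). If Screening replaces a missing Day 1 value, the two covariates coincide for that participant. SAP 6.4 also leaves unnamed other biomarkers to descriptive summary, so some listed markers may never be modelled. These points call for rules in the fix; they do not remove the case for it.

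The liver-injury baseline is weak as a precedent, since it serves individual safety evaluation. A reader might infer that it contradicts the SAP baseline. It does not, because the Protocol confines it to that purpose.

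**Conclusion.** The point holds as a minor, low-cost gain in precision for exploratory markers with two scheduled pre-dose values. The possible fall in residual variance is about 0–20%: 11–20% under equal correlations of 0.5–0.8, 1.8–10.7% over the Case B grid (about 4–6% in its middle), and 0 under pure serial decay. Even the most favourable of these shrinks the standard error by only about 10%.

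A reader might infer that this trial is giving up 11–20% of variance, or the equivalent of 12–25% more participants. The documents do not support that: they report no correlation for any of these markers, and equal correlation is the favourable assumption. Nor should one infer that the exploratory models are affected in general. MRI-PDFF and MRE have a pre-dose value at Screening only, and ELF and the questionnaires at Day 1 only. The primary and secondary biopsy endpoints are outside the point altogether.

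The common baseline slope across visits is a separate restriction that has not been quantified. It matters only where several post-baseline visits are modelled. Metabolic markers have just Weeks 24 and 48, so an analysis through Week 24 has no common-slope issue for them.

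**What to change.** In SAP 6.4:

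- Name the markers to be modelled and state the ANCOVA covariates.
- Keep the response as change from Day 1 and keep Day 1 as a covariate. For modelled markers measured at both visits (candidates: PRO-C3, adiponectin, ALT, AST, LDL, HDL, triglycerides, glucose, insulin, HbA1c, weight, waist), add the Screening value as a second covariate. Do not substitute the two-sample mean for Day 1.
- Add baseline-by-visit terms where more than one post-baseline visit is in the model.
- Prespecify which Screening value is used after retests or carry-over from MB130-069, for example the first valid central-laboratory value that is not itself serving as the Day 1 baseline, with an equivalent rule for weight and waist, which are site measurements.
- If only one pre-dose value exists, use it for both covariates.

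In the Protocol, reconcile the PRO-C3 and adiponectin schedule in 8.5.1 with Tables 1 and 8.

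The cost is a few degrees of freedom and a short SAP paragraph. No new samples, visits or participants are needed. The wording should be settled before those writing it see unblinded marker data.
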